1. PROTOCOL REVISION HISTORY

Rev No	History	Reason			
00	01.07.2021	First version (v1.0)			
01	05.10.2021	Second version (v1.0) - Moved the research starting date forward			

2.2. Supporting Legal Representative

Only the sponsor has the authority to sign. There is no legal representative.

1. ABBREVIATIONS

DR: Diabetic retinopathy

mtmDR: more than mild diabetic retinopathy

vtDR: vision-threatening DR - Vision threatening diabetic retinopathy

ML: Machine learning

ORF: Case Report Form

ADE: Adverse Device Event

UADE: Unanticipated Adverse Device Effects

EDC: Electronic Data Capture

2. LOGIN

2.1. Research Design

This study is a prospective safety/efficacy study.

In the European Union, approximately 32.7 million adults were found to have diabetes in 2017. It is also estimated that 12.8 million people have undiagnosed diabetes. The age-standardized prevalence of diabetes among adults was 6% on average in EU countries in 2017. This rate is 11.9% for our country, which corresponds to approximately 9.6 million diabetic patients. Diabetes has high morbidity and there are millions of people who need to be screened for diabetic retinopathy (DR). The number of ophthalmologists is insufficient corresponding to the high patient density that needs to be screened.

Diabetic retinopathy is a retinal disease that can often be stopped with an early diagnosis but can lead to severe vision loss, including permanent blindness, in case of neglect. The diagnosis and stage of the disease can often be made only through fundus examination or fundus photographs. Artificially intelligent retinal diagnostic softwares present a solution to the shortage of trained ophthalmologists, the evaluation of retinal photographs taken by an ophthalmologist in another center and making a diagnosis (telemedicine - telemedicine); Recently, by using artificial intelligence algorithms, it has become possible to obtain meaningful information from large volumes of data (more from scanned patients/fundus photos) in a shorter period of time with much less human intervention. With the artificial intelligence algorithm in which pathological lesions are taught by using posterior pole photos of the eye, DR lesions are identified with high accuracy and reliability, faster, and at a lower cost. This offers an excellent screening advantage for the early diagnosis and treatment of DR and other retinal diseases.

Methods and tools to be used in the research:

- i. Fundus photography with non-mydriatic camera and classification of diabetic retinopathy with artificial intelligence algorithm
- ii. Evaluation of images by retina specialists and comparison of results for clinical validation of the system.

Clinical and laboratory tests to be performed:

- i. Fundus photography with a non-mydriatic camera. In this examination, a non- invasive procedure is applied to the patient. The retinal photographs will be taken with special digital cameras called 'fundus cameras'. In patients whose non-mydriatic images cannot be obtained, tropicamide drops will be instilled to dilate the pupil, and then photographs will be taken.
- ii. Pupil dilation will be achieved by instilling Tropicamide drops in both eyes of the patient, and then 4 quadrant photographs of both eyes will be taken with a mydriatic fundus camera.

Among the patients admitted at the Akdeniz University Endocrinology and Metabolic Diseases Department with a diagnosis of diabetes, those who want to participate in the clinical study will be referred to the clinical study by the endocrinology polyclinic. The authorized nurse involved in the clinical study will explain the study to the volunteer and ask for the consent form to be signed, and consent will be obtained. Fundus images will be taken with a non-mydriatic fundus camera by a designated technician. Ural Telekom firm, EyeCheckup project and Assoc. [name] is planned to diagnose and classify the images in terms of DR with the artificial intelligence (AI) algorithm developed with the consultancy of [name]. Images obtained using eye drops will be evaluated by the faculty members of the Department of Ophthalmology, Retina Unit, and compared with AI to determine sensitivity and specificity. In this way, it will be possible to screen millions of diabetic patients who need to be screened for diabetic retinopathy in much shorter intervals and with less manpower.

The research will be carried out in a single center at Akdeniz University Faculty of Medicine. The control group will not be used. The EyeCheckup software used in the clinical study does not have a CE mark. However, the Fundus cameras used to take retinal images from the patient in the clinical study are CE-marked and EyeCheckup does not have any direct interaction with the patient. Since the performance and effectiveness of our EyeCheckup software will be measured in the study, the study will be conducted as a Non-CE Marked Medical Device Research (Excluding Thesis and Academic Studies).

The duration of the study is planned to be 12 months, but the study may be terminated if the artificial intelligence algorithm is validated and the intended number of 900 volunteer patients is reached in a shorter time. Since fundus images of the patients will be used, follow-up time is not required. The planned trial time is a maximum of 30 minutes per patient.

There is no other diagnosis/treatment method to be applied together. It is only a study to diagnose DR.

3. STUDY SUMMARY

[figure not shown]
3.1. Summary of Clinical Findings

All documents required by the standard for EyeCheckup software have been created, risk analysis has been made and precautions have been taken against possible risks.

EyeCheckup clinical trial will be performed in a single center at Akdeniz University Hospital. The target population is people aged 18 and over, who have been diagnosed with diabetes in the Endocrinology Clinic of Akdeniz University Hospital and have not been diagnosed with diabetic retinopathy (DR) before, and whose retinal image can be taken. To better align the analysis population with the proposed target population, those who do not meet certain additional predetermined criteria (eg: less than 18 years of age, visually impaired) will be excluded. Volunteers will be taken to the research area allocated by the hospital at Akdeniz University. Before any volunteers are recruited, candidates will need to verify that they understand the research and have given written informed consent. Study; **CE marking will** be made to measure the success of Artificial Intelligence software in terms of specificity and sensitivity, which detects the presence of mild DR (mtmDR) and vision-threatening DR (vtDR) for each eye by taking retinal images from 3 different fundus cameras and using these images.

The artificial intelligence model was trained with fundus images taken from Akdeniz University Hospital Ophthalmology Clinic with the approval of the Akdeniz University Ethics Committee.

The publicly available Kaggle Diabetic Retinopathy Detection Competition (EyePACS dataset), Kaggle APTOS 2019 Blindness Detection Competition dataset, Messidor, Messidor 2, IDRiD Dataset, and DIARETDB0 - Standard Diabetic Retinopathy Database datasets were used as test datasets. A retrospective study was performed on a total of 4000 test images (dataset). As a result of the test studies, more than 92% specificity and 92% sensitivity were obtained. The result of the most successful algorithm is listed below. The most successful algorithm was built on the Google ML Platform, and this first prototype will be used as a Non-CE Marked Medical Device Research (Excluding Thesis and Academic Studies).

Diagnosis	Truth
normal eye	97.19%
Mild/Moderate Diabetic Retinopathy	96.43%
Severe / Proliferative Diabetic Retinopathy	100.00%
Diabetic Macular Edema	100.00%

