3.8. Research Population

All adult patients (male-female) aged 18 years and over who were diagnosed with diabetes but not diagnosed with diabetic retinopathy by the endocrinology outpatient clinic.

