3.9. Inclusion Criteria for Volunteers

Fundus images of 900 volunteer patients with evaluable quality, with or without pathology, who applied to Akdeniz University Endocrinology and Metabolism Diseases Department with the diagnosis of diabetes, who were not diagnosed with Diabetic Retinopathy before and whose images can be taken from the posterior polar region of the eye with a fundus camera, will be included in the study.

- Diabetes must have been diagnosed
- Diabetic Retinopathy must not be diagnosed yet,
- The participant must understand the study and have signed informed consent,
- No history of any other retinal vascular disease, cataract, or other diseases that may affect the appearance of the retina or optic disc (refractive defect and ocular surface disease are allowed),
- No history of intraocular surgery other than cataract surgery, ocular laser therapy for any retinal disease, or ocular injection for diabetic macular edema or proliferative disease,
- No ambient blur preventing good retina photography
- Persons aged 18 and over are included in the study.

If at least one of these conditions is not met, the participant is not included in the study.

[one] Inan, UU, F. Ozturk, and SS Ermis, Pharmacologic pupil dilation in diabetic patients. Retina, 2003. 23(2): p. 254-6

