3.10. Exclusion Criteria for Volunteers

Fundus images that have corneal or lens opacification that will prevent imaging, and that are not evaluable due to intravitreal hemorrhage or vitreous will not be included in the study. Patients followed or treated for DR will not be included in the study.

- If the volunteer are not diagnosed with diabetes,
- If the potential participant cannot understand the study or informed consent,
- If the volunteer has a history of retinal vascular disease other than diabetic retinopathy, glaucoma, or any other disease that may affect the appearance of the retina or optic disc.
- If the volunteer have had previous intraocular surgery including than cataract, laser intervention on the retina, or previous intraocular intervention for the treatment of diabetic retinopathy,
- If there is a permanent visual impairment in one or both eyes,
- If under the age of 18,

- If the participant is contraindicated for imaging with the fundus imaging systems used in the study,
- Exclude if there is an ambient blur in both eyes severe enough to impede good retinal photography.

If at least one of the above conditions is present, the participant is not included in the study.

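### No eligibility rule or analysis identifies participants whose earlier eye-clinic images trained the algorithm, so some patient-level overlap between training and validation is possible

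*Combined protocol and SAP*

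**What the plan says.** On the source of the training data, Section 3.1 says: "The artificial intelligence model was trained with fundus images taken from Akdeniz University Hospital Ophthalmology Clinic". The same section fixes the validation site: "EyeCheckup clinical trial will be performed in a single center at Akdeniz University Hospital".

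Recruitment runs through endocrinology rather than the eye clinic. Section 2.1 draws volunteers from "Among the patients admitted at the Akdeniz University Endocrinology and Metabolic Diseases Department with a diagnosis of diabetes", and Section 3.8 describes the population as adults "who were diagnosed with diabetes but not diagnosed with diabetic retinopathy by the endocrinology outpatient clinic".

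Several rules narrow who can enter:
- Section 3.9: "Diabetic Retinopathy must not be diagnosed yet".
- Section 3.10: "Patients followed or treated for DR will not be included in the study".
- Section 3.10 also excludes other retinal vascular disease, "glaucoma, or any other disease that may affect the appearance of the retina or optic disc".
- Section 3.11 repeats that patients with an existing DR diagnosis are not included.

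The trial images are taken prospectively. Section 2.1: "Fundus images will be taken with a non-mydriatic fundus camera by a designated technician". Section 3.5 sets the reference standard as a majority vote of three doctors. Success requires overall agreement above 90%, counted over eyes, and sensitivity and specificity each above 90% for mtmDR and for vtDR.

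None of Sections 3.8 to 3.11, Section 6 or Annex-1 mentions whether a participant's earlier images were used to build the algorithm.

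**The concern.** A validation sample should be independent of the data on which the model was fitted. Here both come from one hospital, and a diabetic patient can attend endocrinology and the eye clinic there. If such a patient was photographed in the eye clinic, judged free of DR and used in training, the present rules let that patient enrol. The model has then already been fitted to that eye's vessels, disc and pigmentation, and its agreement with the reference may be better than in a patient it has never seen.

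Because known DR is excluded, the overlap would sit mostly among eyes without DR. The quantities at risk are therefore specificity and the overall success rate, both judged against 90%. Sensitivity is exposed only where a training patient has since developed DR or had DR that was never recorded.

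Timing also matters. Section 3.6 says that images are recorded anonymously. If the check is not made at screening, overlap may be hard to trace afterwards.

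**Working it through.** **Step 1. Which training patients can still enrol?**

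| Earlier eye-clinic patient used in training | Eligible under the current text? |
|---|---|
| Diagnosed with, followed for or treated for DR | No (3.9, 3.10, 3.11) |
| Glaucoma, other retinal vascular disease, other disease changing the retina or disc | No (3.9, 3.10) |
| No diabetes | No (3.9, 3.10) |
| Diabetes, photographed, no DR or other excluded eye disease | Yes |

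Only the last row is open. Section 3.9 allows refractive defects and ocular surface disease, so ordinary reasons for an eye-clinic visit do not close it. The documents do not give the number of training patients, their diagnoses or the imaging dates. The accuracy table in Section 3.1 has a normal-eye class, which makes it plausible, though it is not stated, that normal eyes were among the training images.

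**Step 2. Reproduce the plan's own figure.** Inputs from Section 6.2 and Annex-1: P0 = 0.90, one-sided alpha 0.05, reject if Z ≥ 1.6449, and N = 778 for P1 = 0.925.

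Cut-off = smallest integer ≥ N·P0 + 1.6449·√(N·P0·(1 − P0)).

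For N = 778: 700.2 + 1.6449 × √70.02 = 713.96, so 714 correct. Exact binomial probabilities of 714 or more are 0.0530 at 0.90 and 0.8004 at 0.925. Both match the plan's table.

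**Step 3. Same rule at the planned enrolment.** For N = 900: 810 + 1.6449 × 9 = 824.80, so 825 correct. P(X ≥ 825 | 900, 0.90) = 0.0508. This is the chance of passing for a device truly at 90% with no overlap.

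**Step 4. Add overlap.** Let f be the share of overlapping participants and a the accuracy in them. Accuracy in all others is 0.90. Then

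p = f·a + (1 − f)·0.90, and the chance of passing is P(X ≥ 825 | 900, p).

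Both f and a are assumptions; the documents give neither.

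| f | p if a = 0.95 | Chance of passing | p if a = 1.00 | Chance of passing |
|---|---|---|---|---|
| 0 | 0.9000 | 5.1% | 0.900 | 5.1% |
| 1% | 0.9005 | 5.6% | 0.901 | 6.2% |
| 5% | 0.9025 | 8.2% | 0.905 | 12.7% |
| 10% | 0.9050 | 12.7% | 0.910 | 26.4% |
| 20% | 0.9100 | 26.4% | 0.920 | 67.1% |

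Some values recur because only the product f·(a − 0.90) matters.

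**Step 5. Limits of the calculation.** It treats 900 units as independent, whereas Section 3.5 counts eyes, up to 1,800 and correlated within patient. It concerns the overall-success test alone, not the separate sensitivity and specificity requirements.

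**The case against.** The strongest reply is that no training image or training label is reused. The photographs are new, and the reference is a fresh three-doctor vote on dilated images (Sections 3.4 and 3.5). Any leakage would require the model to profit from having seen the same eye in a different photograph, which is a weaker mechanism than re-scoring training data. This stands, and it is why the 100% column is an upper bound. Section 3.1 itself reports 97.19% for normal eyes in the earlier test.

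A second reply is that the eligible overlap group may be negligible. The documents cannot rule that out. At 1% overlap the chance of passing hardly moves.

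Third, overlap among DR-free eyes cannot lift sensitivity, which must also exceed 90%. A device helped over the overall-success line could still fail the trial. This stands too.

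A reader might infer that nothing keeps training patients out. The text does not support that: Sections 3.9 to 3.11 remove those with known DR, glaucoma or other retinal disease. A reader might also infer that the validation set contains training images. It does not, because the images are taken prospectively.

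These replies limit the scope and likely size of the problem. They do not supply the missing check. Recruiting through endocrinology does not separate the two groups of patients, and the earlier test on public datasets says nothing about who enters this trial.

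**Conclusion.** The gap is real but narrow: a safeguard is missing, and no stated figure is wrong. The plan as written admits diabetic patients of this hospital whose earlier eye-clinic images may have been used in training, provided they have no diagnosed DR or other excluded eye disease, and nothing in the analysis would reveal them.

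The true bias cannot be computed from the documents. Under the stated assumptions, overlap of 1% to 20% raises the chance of a false pass on the overall-success test from 5.1% to between 5.6% and 26.4% if overlapping patients are classified at 95%. If they are classified at 100%, the range is 6.2% to 67.1%. The last figure needs both extremes at once and should not be read as an estimate. The case for acting rests on the low cost of the safeguard, not on evidence that overlap is large.

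**What to change.** Add one exclusion to Section 3.10: *any patient whose fundus images were used to train or tune EyeCheckup*. Apply it by checking hospital identifiers against the training list at screening. Section 3.3 already schedules eligibility and medical-history review at the visit, so the check fits there.

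If training identifiers were not kept, record whether each participant had eye-clinic photography before the training cut-off date. Then specify in Annex-1 that the primary analysis is repeated without those participants.

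The cost is a record check per candidate and a few candidates replaced or, under the fallback, one sensitivity analysis.

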3.2. Study Schedule and Duration

Baseline (first patient enrollment): 01 November 2021

End (last patient to complete study): 01 November 2022

3.3. Flow Chart of Study

Visit	Scanning Day 1, Visit 1	Registration/Basic Day 1, Visit 1	Run Termination Day 1, Visit 1
Be Informed	х	x	x
Inclusion/Exclusion Criteria	х	х	х
Demography	х	x	x
Medical History (Additional Disease History)	х	х	х
Study Intervention	х	х	х
Dilated Ophthalmoscopy	х	х	х
Full Case Report Forms (Orfs - E-Orf)		х	х
Adverse Events			х

3.4. Rationale / Importance and Contribution of the Research

EyeCheckup is an automated software instrument designed to analyze digital color photographs of the ocular fundus to quickly screen for diabetic retinopathy (DR).

The main purpose of the study was to detect the presence of mild diabetic retinopathy or sight-threatening diabetic retinopathy from retinal fundus images in adult patients who applied to the endocrinology outpatient clinic due to diabetes, to grade and to determine the sensitivity and specificity of diabetic retinopathy, and to identify and classify the images with the developed

artificial intelligence algorithm. It is a comparison of diagnosis done by artificially intelligent algorithms and classification of DR done by doctors.

The primary efficacy endpoint in the study was that EyeCheckup's intended image capture workflow could be successfully used in conjunction with the EyeCheckup device to diagnose 80% or more of the participants for more than mild diabetic retinopathy (mtmDR) and vision-threatening diabetic retinopathy (vtDR) separately with a minimum 90% sensitivity and 90% specificity.

The secondary efficacy endpoint in the study was

Additional non-primary analyzes will also be performed to assess the following general conditions:

- Positive Predictive Value of EyeCheckup test for mtmDR and vtDR,
- Negative Predictive Value EyeCheckup test for mtmDR and vtDR.
- Positive and negative odds ratios for mtmDR and vtDR.

The study will include approximately 900 people with diabetes, excluding exclusions. They will be recruited voluntarily through 1 clinical center. Two photographs of the ocular fundus (one optic disc centered, one macula centered) will be obtained per eye using a non-mydriatic eye fundus camera from both eyes of the participants. These images will be analyzed by EyeCheckup. Then, pupil dilation will be achieved by instilling Tropicamide drops in both eyes of the patient and 4 quadrant photographs of both eyes will be taken with a fundus camera. Ophthalmologists will then evaluate and record the condition of the eyes based on images obtained with pupil dilation.

There is no similar or equivalent product in our country. It is the first locally produced and developed product. Equivalent FDA-approved and CE-marked products are available abroad. Similar clinical studies have been conducted with equivalent products abroad. Detection and classification of diabetic retinopathy is planned in the first version of our product. In the next stages, we aim to detect more than 20 diseases, including glaucoma, cataract, and age-related macular degeneration, by developing the product. Most similar products only work in the field of diabetic retinopathy.

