3.5. Success Criteria of Study

Three different doctors will evaluate the volunteer's fundus images taken from fundus cameras and will make a decision about the presence of DR: Not more than Mild DR, More than mild DR (mtmDR), and Vision-threatening DR (vtDR). Decisions will be made by majority vote. The doctors' decision will be Ground Truth for us.

EyeCheckup will decide for both eyes of each volunteer. If it is the same as the doctors' decision, this decision will be considered correct.

Total correct number / Total number of eyes = Success rate

Our criteria for successful completion of the clinical trial: Success rate > 90%

EC-2021DR-TR DETECTION AND CLASSIFICATION OF DIABETIC RETINOPATHY FROM POSTERIOR POLE IMAGES WITH A DEEP LEARNING MODEL

At the same time, the Specificity and Sensitivity values should be calculated separately for mtmDR and vtDR and each should be above 90%.

Eye doctors (Normal, mtmDR, vtDR) make their decisions according to the ETDRS guidelines. Main signs to check for: Microaneurysms, Intreretinal hemorrhages (Intraretinal hemorrhage), Venous beading, IRMA, Neovascularization, Intravitreal hemorrhage, Preretinal hemorrhage

3.6. The benefit of the Research, Possible risks and precautions to be taken against harm:

Benefits;

According to the 2018 data from the World Health Organization, 285 million people worldwide have a visual impairment. It is known that more than 80% of all visual disorders can be prevented or treated. The retinal examination should be performed by an ophthalmologist and/or retinal specialist in order to prevent retinal-related visual disorders by making an accurate diagnosis, but people only consult an ophthalmologist when they feel any discomfort. Typically, by the time symptoms appear, the disease has reached advanced stages and requires a variety of expensive medical and surgical treatments. Unfortunately, at this stage, the disease often results in severe and permanent visual impairment and vision loss.

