6. STATISTICS

6.1. Analysis

Fundus images of 900 volunteer patients with evaluable quality, with or without pathology, who applied to Akdeniz University Endocrinology and Metabolism Diseases Department with the diagnosis of diabetes, were not diagnosed with Diabetic Retinopathy before, and whose images can be obtained from the posterior polar region of the eye with a fundus camera, will be included in the study, which will be carried out as a single-center study. The sample size was determined by Akdeniz University Statistics Consultancy Application and Research Center, taking into account the incidence of diabetic retinopathy in diabetic patients. Upon confirmation that the Al algorithm is working successfully, the trial will be terminated when the intended number of 900 patients is reached. The success criterion of the study is specified in Article 3.5.

The classification performance of the AI algorithm will be evaluated with reference to the diagnosis made by the doctors. Gold standard test results will be obtained based on the diagnosis from three different doctors. At this stage, the compatibility between the diagnosis from the doctors will be evaluated according to the Kappa statistics, and the similarity of the decisions made by the doctors with each other will be examined. The diagnoses of the patients will then be evaluated together with the results of the AI algorithm, and performance measures of the AI algorithm (sensitivity, selectivity, positive predictive value, negative predictive value, overall accuracy, etc.) will be obtained. Whether the performances of the AI algorithm are clinically acceptable or not will be evaluated with ratio tests (single sample population ratio significance test, Fisher Exact test, Chi-square tests, etc.) according to the threshold values to be determined by experts. A data analysis software will be selected among various software (R, SPSS, TURCOSA, Stata, etc.) to do the statistical analysis in accordance with the purpose. For statistical analysis, the level of significance will be taken as 0.05. (Annex-1 Analysis Plan)

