ANNEX-1 ANALYSIS PLAN

The diagnosis of the patients will be made by 3 doctors by evaluating the images and a joint diagnosis decision will be made by combining the diagnosis made by the doctors for each patient. This diagnosis will be considered the "Gold Standard" for the study. With the developed Al algorithm, it will be investigated to what extent the diagnosis made by the doctors can be predicted. The Al algorithm developed for the diagnosis of DR is expected to achieve a success rate of 90% or more. A success above this level will show that the developed Al algorithm will be usable. For this purpose, whether the Al algorithm achieves a success rate of 90% or more will be investigated with the one-way hypothesis pair given below.

$$H_0: P = 0.90 H_1: P > 0.90$$

The sample size was calculated by evaluating whether the Al algorithm achieved a success rate of more than 90%, considering 5% Type-I error, 80% power, and different effect sizes listed below.

Prop	ortion	Proportion					
_		Given H0	Given H1	Target	Actual		Reject H0
Power	N	(P0)	(P1)	Alpha	Alpha	Beta	If Z>=This
0,8033	5341	0,9000	0,9100	0,0500	0,0511	0,1967	1,6449
0,8002	2286	0,9000	0,9150	0,0500	0,0520	0,1998	1,6449
0,8015	1255	0,9000	0,9200	0,0500	0,0525	0,1985	1,6449
0,8004	778	0,9000	0,9250	0,0500	0,0530	0,1996	1,6449
0,8012	523	0,9000	0,9300	0,0500	0,0541	0,1988	1,6449
0,8047	376	0,9000	0,9350	0,0500	0,0545	0,1953	1,6449
0,8092	284	0,9000	0,9400	0,0500	0,0539	0,1908	1,6449
0,8076	212	0,9000	0,9450	0,0500	0,0565	0,1924	1,6449
0,8004	164	0,9000	0,9500	0,0500	0,0553	0,1996	1,6449

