The diagnostic performance of the AI algorithm will be evaluated with reference to the decisions made by the doctors. Gold standard test results will be obtained based on the diagnosis provided by three different doctors. At this stage, the compatibility between the diagnosis from the doctors will be evaluated according to the Kappa statistics, and the similarity of the diagnosis made by the doctors with each other will be examined. The diagnoses of the patients will then be evaluated together with the results of the AI algorithm, and performance measures of the AI algorithm (sensitivity, selectivity, positive predictive value, negative predictive value, overall accuracy, etc.) will be obtained. Whether the performances of the AI algorithm are clinically acceptable or not will be evaluated with ratio tests (single sample population ratio significance test, Fisher Exact test, Chi-square tests, etc.) according to the threshold values to be determined by experts. A data analysis software will be selected amongst various softwares (R, SPSS, TURCOSA, Stata, etc.) to do the statistical analysis in accordance with the purpose. For statistical analysis, the level of significance will be taken as 0.05.

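### The requirement in 3.4 that 80% or more of participants be diagnosed is missing from the success criteria and the analysis plan, and the evaluable-image rule probably removes failures from its denominator

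*Combined protocol and SAP*

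**What the plan says.** **The endpoint.** Section 3.4 states a compound primary efficacy endpoint. The intended capture workflow with EyeCheckup must be usable "to diagnose 80% or more of the participants for more than mild diabetic retinopathy (mtmDR") and, separately, for vtDR, with sensitivity and specificity of at least 90%. The same section sizes the trial: "The study will include approximately 900 people with diabetes, excluding exclusions".

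**The success rule.** Section 3.5 reads "Our criteria for successful completion of the clinical trial: Success rate > 90" (per cent), and adds that sensitivity and specificity must each exceed 90% for mtmDR and vtDR. The success rate is correct decisions over total eyes, and "EyeCheckup will decide for both eyes of each volunteer". The 80% share does not appear. Section 6.1 then says "The success criterion of the study is specified in Article 3.5".

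**The analysis.** Annex-1 has one hypothesis pair: whether the algorithm "achieves a success rate of 90% or more will be investigated with the one-way hypothesis pair given below", with P = 0.90 against P > 0.90. Its measures are those of accuracy: "sensitivity, selectivity, positive predictive value, negative predictive value, overall accuracy, etc.) will be obtained".

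**Who is counted.** Sections 3.9 and 6.1 define the 900 as patients with fundus images of evaluable quality. Sections 3.10 and 3.11 drop images that cannot be evaluated for named causes (corneal or lens opacity, haemorrhage, vitreous), and 3.10 excludes people with severe blur in both eyes. Section 9.2 puts consent before any study activity. In 2.1, photography follows consent: "Fundus images will be taken with a non-mydriatic fundus camera by a designated technician". Item i of the tests listed in 2.1 provides a repeat after dilation where the non-mydriatic image cannot be obtained.

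**The concern.** The 80% component is a claim about the workflow: of the people on whom it is tried, how many get an answer. Two features of the plan undercut it.

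First, the rule that governs success omits it. A team that follows 3.5, 6.1 and Annex-1 to the letter can report success without ever computing it, although 3.4 calls it part of the primary endpoint.

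Second, if the share is computed among the 900 as 3.9 and 6.1 define them, people whose photographs could not be evaluated may already have been removed. What remains is mainly the software's no-result rate, which is a different and easier quantity. If nobody records the failed attempts, the right denominator may not be recoverable later.

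**Working it through.** **1. The plan's own calculation.** The marked row in 6.2 and Annex-1 has N = 778, P0 = 0.90, P1 = 0.925, power 0.8004 and actual alpha 0.0530. The test rejects when the count reaches 0.90 × 778 + 1.6449 × √(778 × 0.90 × 0.10) = 713.96, that is, at 714 correct. The exact binomial gives P(X ≥ 714) = 0.0530 at 0.90 and 0.8004 at 0.925. The figure reproduces, and it concerns the 90% success rate only. The 80% in that text is power and has nothing to do with the 80% of participants in 3.4.

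**2. Where the component appears.**

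| Place | 90% success rate | Sensitivity, specificity | 80% of participants |
|---|---|---|---|
| 3.4 primary endpoint | no | yes | yes |
| 3.5 success criteria | yes | yes | no |
| 6.1 | by reference to 3.5 | listed as measures | no |
| Annex-1 | yes, one hypothesis | listed as measures | no |

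**3. What 3.5 already guarantees among included participants.** Read 3.5 literally: every eye of every included volunteer is in the denominator, and an eye with no result is not correct. Let f be the share of eyes without a result. Then:

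- success rate ≤ 1 − f, so a success rate above 0.90 forces f < 0.10;
- participants with at least one no-result eye ≤ 2f, so the share with both eyes diagnosed ≥ 1 − 2f > 0.80.

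With 900 participants and 1,800 eyes, success needs at least 1,621 correct. At most 179 eyes have no result, so at least 900 − 179 = 721 participants (80.1%) have a result in both eyes. Among included participants, 3.5 therefore implies the 80%, whichever eye rule is used.

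**4. What 3.5 does not guarantee.** Step 3 says nothing about people attempted and then removed for image quality. The documents give no failure rates, so the numbers attempted below are assumptions. They take 900 evaluable participants, all with an EyeCheckup result, and exact (Clopper-Pearson) 95% intervals.

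| Attempted | Share = 900 / attempted | 95% CI | Share if only the 900 count |
|---|---|---|---|
| 1,000 | 90.0% | 88.0–91.8% | 100% |
| 1,125 | 80.0% | 77.5–82.3% | 100% |
| 1,200 | 75.0% | 72.4–77.4% | 100% |

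Since 900/1,126 = 79.9%, 1,125 is the largest number attempted that still meets the criterion; beyond it, more than 20% of attempts have failed. The last column is the same in every row: with the evaluable-only denominator the component cannot tell these cases apart.

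**5. Adding software no-results.** The two losses multiply. With 10% capture failure (assumed), the share falls below 80% once more than 1 − 0.80/0.90 = 11.1% of evaluable participants lack a result.

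**The case against.** The best defence is step 3: 3.5 applies to both eyes of each volunteer, so a trial that passes 3.5 already has more than 80% of included participants diagnosed. This stands, on the literal reading. A reader might infer that the choice between one eye and both eyes can by itself turn a successful trial into a failed one; for included participants the documents do not support that. The defence stops at inclusion, however, and depends on no-result eyes staying in the denominator, which 3.5 does not say outright.

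A reader might also infer that the dilated repeat is an open loophole. Section 2.1 places it inside the non-mydriatic photography procedure, so the natural reading is that a result obtained that way counts.

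The evidence for late exclusion is also limited. Sections 3.10 and 3.11 name particular causes, some of which can be seen before imaging, and blur excludes only when it affects both eyes. Only the evaluable-quality wording in 3.9 and 6.1 is general. The flow chart in 3.3 marks nearly every row in all three columns of the same visit, so it proves little. This is why the denominator problem is stated as the natural reading and not as a fact.

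Finally, 3.1 defines the target population as people whose retinal image can be taken, which makes accuracy in evaluable eyes a legitimate quantity. That is accepted; the gap concerns the workflow claim only. The open-ended list of measures and tests in 6.1 and Annex-1 does not fill it, because that text is about the algorithm's performance against the doctors' diagnosis.

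**Conclusion.** The point holds in this form: a stated part of the primary endpoint is absent from the success criteria and the analysis plan, and the way the 900 are defined probably removes at least some imaging failures from its denominator. Success can then be declared with the workflow share unmeasured, or measured on a set where it is near 100% apart from software no-results.

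The size cannot be fixed from the documents. Under the assumptions in step 4, the true share is 90% when 1,000 are attempted and drops below 80% only beyond 1,125. Nothing in the plan suggests a failure rate above 20%, so a reader should not conclude that the trial would miss the 80%. Nor do the documents show an intention to drop every failed attempt.

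Severity: should-fix, before enrolment, since failed attempts that are not logged may be lost.

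**What to change.** 1. **Log attempts.** Record every consented participant who meets the criteria that can be judged before photography and in whom photography is attempted, noting capture failure, use of the dilated repeat and software no-result.
2. **Define the component.** The numerator is participants with an EyeCheckup result in both eyes (following 3.5) after the full procedure in 2.1, including the dilated repeat. The denominator is all attempted participants in the log. Report the share with an exact confidence interval, show it also without dilated repeats, and add it to 3.5, 6.1 and Annex-1 so that they agree with 3.4.
3. **Separate the two sets.** Treat non-evaluability found at photography as exclusion from the accuracy set only. State in 3.5 that no-result eyes of included volunteers count as not correct. Note that the 80% component is measured in attempted participants, a wider group than the 3.1 population.

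A further sensitivity analysis of accuracy for no-result eyes is optional.

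**Cost.** Wording in 3.5, 3.9 to 3.11, 6.1 and Annex-1; keeping the log; and a somewhat lower reported imageability. Sections 3.9 and 6.1 already ask for 900 evaluable, so on that reading nobody extra is photographed. If the site had planned to stop at 900 photographed, report the share among those 900 and do not enrol more.
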